## 1. SYNOPSIS

Sponsor: Grupo Español Multidisciplinar en Melanoma - GEM

Investigational Products: Encorafenib and binimetinib

Active Ingredients: Encorafenib and binimetinib

**Title of Study:** Phase II, multicentre clinical trial to evaluate the activity of encorafenib and binimetinib administered before local treatment in patients with BRAF mutant melanoma metastatic to the brain.

Protocol number: GEM-1802

EudraCT: 2018-002530-20

Study center(s): 21 sites in Spain. In attached document

## Studied period (years):

Estimated date first patient enrolled: 3Q 2019 (19.JUL.2019)

Estimated end of enrolment: 3Q 2022

Estimated date last patient completed: 3Q 2024

Phase of development:

Ш

## **Objectives:**

## 1. Primary objective:

Intracranial objective response rate assessed by the investigators using modified RECIST criteria before local treatment in cohort 1 and in cohort 2.

2. Secondary objectives:

- a.Intracranial objective response rate assessed by the investigators using modified RECIST criteria. before local treatment in cohort 2.
- b. Intracranial objective response rate assessed by the investigators using modified RECIST criteria, before local treatment in cohort 1.
- c.The duration of the intracranial response in both cohorts assessed by the investigators using modified RECIST criteria.
- d. The intracranial progression free survival assessed by the investigators using modified RECIST criteria in both cohorts.
- e. Percentage of patients free of intracranial progression according to modified RECIST criteria at 6 (week 24), 12 (week 48) and 24 months (week 96) in both cohorts
- f. Percentage of patients free of extracraneal progression according to RECIST criteria at 6 (week 24), 12 (week 48) and 24 months (week 96) in both cohorts
- g. Overall survival in both cohorts
- h.Percentage of alive patients at 6, 12 and 24 months in both cohorts
- i. Toxicity of the combination until local treatment in both cohorts
  - I. Toxicity of the combination after local treatment in both cohorts
  - II. Quality of life in both cohorts

## Methodology:

This is a phase II clinical trial, with two cohorts of patients included in parallel, all with melanoma BRAF mutated and brain metastases without previous local treatment in the brain. Cohort 1 will include patients with asymptomatic brain metastases and cohort 2 will include patients with symptomatic brain metastasis.

BRAF mutation status will be tested locally using a validated test before patient inclusion, patients will receive both encorafenib 450 mg/day and binimetinib 45 mg/12 h (twice a day) (COMBO450) until progression disease (PD), toxicity or death. After 56 days of treatment, a contrast enhanced brain MRI and body CT scan will be performed as the first tumour assessment. Depending on the outcome of this image test, patients undergo local radiation treatment (radiosurgery or whole brain radiotherapy (WBRT) as per local radiotherapy oncologist. Encorafenib and binimetinib will be interrupted 24h before radiotherapy and restart 24h after the last dose of radiotherapy. After local treatment encorafenib and binimetinib will be administered at same doses until PD, toxicity or death. After progression, patients will be followed only for overall survival. In the case of COMBO450 is providing a clinical benefit to any patient, treatment could be continued, after agreement with Sponsor.

This study will be carried out following good clinical practices (GCP) guidelines as per European and Spanish regulations for clinical investigations.

Number of patients (planned): At least 63 patients.

Cohort 1: N=48; Cohort 2: N=15.

#### Main eligibility criteria:

- Patients 18 years old
- Patients with a metastatic BRAF V600 mutated melanoma
- ECOG 0-1 in asymptomatic patients (cohort 1), 0-2 in symptomatic patients (cohort 2)
- Previous administration of BRAF and/or MEK inhibitors in the metastatic setting is not allowed. These treatments would be allowed if they were administered in the adjuvant setting, providing relapse does not occur on treatment or within 12 months of ending adjuvant treatment and/or during adjuvant treatment, moreover, any grade 3-4 prior toxicity must be resolved to grade 0 or at baseline levels.
- Previous immunotherapy treatments are allowed in any metastatic and adjuvant setting, regardless of when the patient has relapsed.
- At least one brain metastasis with 5 to 50 mm, measured by MRI
- Steroids or anticonvulsants are allowed if clinically needed and are not being administered in an increasing dose

Full list of eligibility criteria is detailed in section 6 of this protocol

## Investigational products, dosage and mode of administration:

#### COMBO450:

- Encorafenib Orally, 75 mg and 50 mg capsules
- Binimetinib Orally, 15 mg tablets

In each cohort, patients will be treated with encorafenib 450 mg once daily and binimetinib (Bini) 45 mg twice daily until PD or death.

#### **Duration of treatment:**

All patients receiving COMBO450 for at least 56 days of treatment, will be evaluated with a contrast enhanced brain MRI and CT body scan, as the first tumour assessment:

 Patients with PD at first evaluation in brain MRI (per RECIST modified criteria) and /or body CT scan (per RECIST 1.1 criteria) will discontinue study drugs and will be followed for overall survival.

- Patients with intracranial complete response (CR) and no systemic PD, will be followed every two months with brain MRI and body CT scan up to 12 months. If no PD after one year, patients will be followed as per institutional criteria, and continue with the study treatment
  - Whenever is considered by the investigator, local treatment can be administered to patients with an intracranial CR.
- Patients with no CR nor PD in brain MRI per modified RECIST 1.1 criteria, and no systemic PD per RECIST 1.1, will be treated with local radiotherapy (RT) (radiosurgery or WBRT), and then they will continue COMBO 450. The first 3 patients with indication to be treated with radiotherapy will be treated in an initial running phase. These three first patients are going to be treated sequentially or at the same time depending on when radiotherapy treatment is needed. If no safety concerns appear, the rest of the patients will continue receiving local treatment when it will be medically indicated:
  - Encorafenib and binimetinib will be interrupted 24h before radiotherapy and restart 24h after the last dose of radiotherapy. The local radiation technique will be defined and indicated by the radiotherapy oncologist (local co-investigator) following the criteria defined below, regarding how to treat patients with the different techniques depending on the number of lesions and its maximum size in the last tumour assessment done during the treatment with encorafenib and binimetinib:
    - \*Radiosurgery (RS) or Stereotactic radiosurgery (SRS):
      - 1 brain metastases < 4 cm
      - ≤ 3 brain metastases ≤ 3 cm
      - ≤ 4 brain metastases ≤ 2.5 cm
    - Whole brain radiotherapy (WBRT):
      - ≥ 4 brain metastases
      - Almost one brain metastasis of ≥ 4 cm
      - ≤ 4 brain metastases not eligible for RS or SRS
      - Metastases located at brain stem, midbrain, pons, and medulla or within 10 mm of the optic nerves and chiasm.
- \*Radiosurgery: for patients who do not meet criteria for radiosurgery (RS) or (SRS), exceptional cases are allowed after prior detailed consultation with the trial coordinators.
  - After the first evaluation of the patient's intracranial response, patients without progression who received a local treatment, could receive other local treatments at the discretion of the investigator, if this is considered beneficial for the patient.
  - Surgery can be done if, as per investigator criteria, is necessary for the patient's health.
  - Patients with an intracranial CR not treated with radiation, if during follow up an only intracranial PD occurs, local treatment will be carried out as per protocol criteria. These patients can continue encorafenib and binimetinib treatment after local treatment if clinical benefit is considered by investigator.
  - All patients progressing by RECIST 1.1 criteria in body CT scan and/or by modified RECIST 1.1. criteria in contrast enhanced brain MRI, after having received local radiation therapy will discontinue systemic treatment with COMBO 450.

#### Criteria for evaluation:

Efficacy assessment will be performed according to modified RECIST 1.1 criteria by contrast enhanced MRI for evaluating intracranial disease and according to RECIST 1.1 criteria by CT scan (PET-CT is also allowed) for evaluating systemic disease, every 8 weeks (+/-1 week) up to 12 months. If no PD during the first year, patients will be followed as per institutional criteria. Image technique should be consistent throughout the study. If no PD is observed after one year of follow up, patients will be followed as per institutional criteria, maintaining the treatment when clinical benefit is observed.

#### Pharmacokinetics:

No pharmacokinetic study will be performed.

## Safety:

Assessment of adverse events, safety, and toxicity will be performed according to the Common Terminology Criteria for Adverse Events (CTCAE - version 4.03) at each patient visit from the time of Informed Consent is signed until the end of the study.

## **Quality of Life:**

EORTC QLQ 30 administered at baseline, at week 8 and week 24.

#### Statistical methods:

The sample calculation has been done for the **primary endpoint (cohort 1)** and it's based on a Fleming's Single Stage Procedure:

We want to show that the Intracranial response rate by modified RECIST 1.1 before local treatment is superior or equal to the reference value, say, 90=40%. Under the hypothesis to have a response rate under new treatment ( $\pi$ 1) of 60% with  $\alpha$  risk = 5% in one-sided test and a power of 80%, the required sample size is 38 patients.

Finally, if 20% of patients will be lost of follow up, die or progress before day 56 without doing the first tumour assessment (according data published in COMBI-MB study), the initial sample size will be 48 patients, to obtain 38 evaluable patients.

Data of study will be analysed in the following populations:

- ITT: All patients that has been enrolled in the trial
- Evaluable population (PP): All patients fulfilling all eligibility criteria and having at least two valid tumour assessments (baseline and one evaluation MRI or CT-scan) without any protocol deviation that makes the patient invalid for the primary endpoint evaluation.
- Safety population: All patients receiving at least one dose of treatment.

Cohort 2 (N=15) is exploratory and no formal sample calculation has been performed, a descriptive analysis will be performed on the same variables and population as cohort 1 (N=48). The only difference is that the population included will be symptomatic. The efficacy and safety as an overall of both cohorts in conjunction will be also addressed.				

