#### 3.0.1. Rationale for primary endpoint

COMBI-MB reported similar treatment activity of BRAF/MEK inhibitors in BRAF V600 mutated melanoma with brain metastasis regardless of symptomatology51. Moreover, recent studies on proposed setting are reporting iORR regardless of symptoms at diagnosis55,56.

We sought to determine as the primary endpoint for this trial the intracranial ORR (iORR) regardless of symptomatology. iORR will be also calculated as initially proposed by cohort, depending on symptomatology.

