## 4.1. Study Hypothesis

The main hypothesis is that:

 Intracranial response rate by modified RECIST 1.1 before local treatment will be ≥40% in cohort 1 and 2.

Study will be considered positive if the main hypothesis is achieved.

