#### 2. Secondary objectives:

[figure not shown]
- a. Intracranial objective response rate assessed by the investigators using modified RECIST 1.1 before local treatment in cohort 2.
- b. Intracranial objective response rate assessed by the investigators using modified RECIST 1.1 before local treatment in cohort 1.
- c. The duration of the intracranial response in both cohorts assessed by the investigators using modified RECIST 1.1.
- d. The intracranial progression free survival by modified RECIST in both cohorts
- e. Percentage of patients free of intracranial progression according to modified RECIST at 6 (week 24), 12 (week 48) and 24 months (week 96) in both cohorts.
- f. Percentage of patients free of extracraneal progression according to RECIST 1.1 () at 6 (week 24), 12 (week 48) and 24 months (week 96) in both cohorts.
- g. Overall survival in both cohorts.
- h. Percentage of alive patients at 6, 12 and 24 months in both cohorts.
- i. Toxicity of the combination until local treatment in both cohorts:
  - Toxicity of the combination after local treatment in both cohorts.
  - Quality of life in both cohorts.

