# 10. STATISTICS

# 10.1. Sample size calculation

# Sample size calculation:

The sample calculation has been done for the **initially proposed primary endpoint (cohort 1)** and it's based on a Fleming's Single Stage Procedure:

We want to show that the Intracranial response rate by modified RECIST 1.1 before local treatment is superior or equal to the reference value, say, 90=40%. Under the hypothesis to have a response rate under new treatment ( $\pi$ 1) of 60% with  $\alpha$  risk = 5% in one-sided test and a power of 80%, the required sample size is 38 patients.

Finally, assuming that, 20% of patients will be lost of follow up, die or progress before day 56 without doing the first tumour assessment (according data published in COMBI-MB study), the initial sample size will be 48 patients, to obtain 38 evaluable patients.

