#### 14. Publication Policy

As stated in article 42 of RD 1090/2015 of clinical trials, the Sponsor is obliged to publish both positive and negative results of the authorized clinical trials in scientific journals and with mention to the Ethical Committee of Clinical Research that approved the study.

After completion of the trial, the clinical publication will be carried out by the Coordinating Investigator in collaboration and Principal Investigators, however interim analysis of preliminary data of primary/secondary endpoints may be published by the Sponsor in scientific meetings and/or Congresses. The order of authors will strictly depend on the number of eligible patients included by the Investigators. Coordinating investigators will be first and last authors, and the number of the rest of the authors will depend on the above rule and the requirements of the congresses and/or journals.

The results will be published in two publications. It is estimated that the first publication will include the results of the analysis of the primary/secondary endpoints and will include data from the symptomatic cohort. The second publication will include the results of the analysis of the primary/secondary endpoints from the asymptomatic cohort and potential comparisons between both cohorts. The Investigator will inform the Sponsor in advance about any plans to publish or present data from the trial. Any publications and presentations of the results (abstracts in journals or newspapers, oral presentations, etc.), either in whole or in part, by Investigators or their representatives will require written authorization by the Sponsor before submission.

The anonymity of the source subjects of the data and biological samples will be maintained at all times. The results or conclusions of the study will be communicated primarily in scientific publications before being released to the non-health public. No efficacy study outcome will be reported prematurely or in a sensationalistic way. Participating investigators should not publish any patient data that is directly related to the study objectives until the trial report is published.

The trial will be registered in the Spanish Registry of Clinical Studies (REEC - Registro Español de Estudios Clínicos) and Clinical trials.gov before including the first patient.

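### The current text conflicts on which population decides the primary endpoint, so the same responses can make the study positive or negative depending on the section applied.

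*Combined protocol and SAP*

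**What the plan says.** **Cohort 1 decides.** The synopsis, under statistical methods, bases the sample size on the "primary endpoint (cohort 1") and continues: "Cohort 2 (N=15) is exploratory and no formal sample calculation has been performed, a descriptive analysis will be performed". The same paragraph ends by saying that both cohorts will also be looked at together, without giving that analysis primary status.

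**Both cohorts together decide.** Protocol 3.0.1: "We sought to determine as the primary endpoint for this trial the intracranial ORR (iORR) regardless of symptomatology". It adds that by-cohort rates will be calculated as well. Section 10.1 keeps the same calculation but relabels it: "The sample calculation has been done for the initially proposed primary endpoint (cohort 1"). Section 10.2 defines the endpoint over cohorts 1 and 2 and adds separate reporting for each. Section 4.2 lists the cohort 2 rate and the cohort 1 rate as secondary objectives a and b, the latter as "b. Intracranial objective response rate assessed by the investigators using modified RECIST 1.1 before local treatment in cohort 1".

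**Not specified.** Section 4.1 gives the hypothesis "Intracranial response rate by modified RECIST 1.1 before local treatment will be ≥40% in cohort 1 and 2" and makes the study positive if it is met. The primary objective (synopsis and 4.2) names cohort 1 and then cohort 2, which can be read as each cohort.

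**SAP.** Sections 4.1 and 4.2 (Tables 40 and 42) show response for all patients, cohort 1 and cohort 2 in turn, for ITT and for PP. No test, critical number or deciding row is given.

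**The concern.** Section 4.1 holds the trial's only success criterion. If the deciding population is not fixed, a reader can apply the synopsis and judge cohort 1, apply 3.0.1 and 10.2 and judge the two cohorts combined, or read 4.1 and 4.2 literally and require both cohorts to succeed. Success could then be claimed on the combined rate when the cohort the trial was sized for has failed, or the reverse. Because the trial is open label and response is read by the investigators, the choice could be made with the results in view. The operating characteristics are also undefined: no sample size or power is stated for the combined endpoint.

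**Working it through.** **Inputs.** Synopsis statistics and protocol 10.1: reference rate 40%, alternative 60%, one-sided 5%, power 80%, 38 evaluable, 20% loss, 48 enrolled in cohort 1. Synopsis: 15 in cohort 2, 63 in total. Assumption: the same 20% loss in cohort 2, so 15 × 0.8 = 12 evaluable and 38 + 12 = 50 pooled. Results are also given for the full 48 and 15.

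**Reproducing the plan's figure.** n = [(z₀.₉₅√(p₀q₀) + z₀.₈₀√(p₁q₁)) / (p₁ − p₀)]² = [(1.645 × √0.24 + 0.842 × √0.24) / 0.20]² = 37.1, rounded up to 38. Then 38/0.8 = 47.5, rounded up to 48. Both figures reproduce, for cohort 1 only.

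**Exact rules.** The critical number is the smallest r with P(X ≥ r | n, 0.40) ≤ 0.05. Power is at a true rate of 60% in both cohorts.

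| Deciding population | Evaluable N: rule | Power | Full N: rule | Power |
|---|---|---|---|---|
| Cohort 1 | ≥21/38 | 78% | ≥26/48 | 83% |
| Combined | ≥27/50 | 84% | ≥33/63 | 91% |
| Each must pass | ≥21/38 and ≥9/12 | 18% | ≥26/48 and ≥10/15 | 34% |

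**Reversals under the exact 5% test.**
- 20/38 + 7/12 = 27/50: cohort 1 fails (p = 0.078), combined passes (p = 0.031).
- 21/38 + 4/12 = 25/50: cohort 1 passes (p = 0.041), combined fails (p = 0.098).

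**Reversals under the literal rule of 4.1 (observed rate at least 40%).**
- 20/48 = 41.7% with 5/15: positive on cohort 1; combined 25/63 = 39.7%, negative.
- 19/48 = 39.6% with 7/15: negative on cohort 1; combined 26/63 = 41.3%, positive.

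**How often cohort 1 and combined disagree.** Sum over all outcomes (x, y) of two independent binomials where exactly one of the two exact tests passes:

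| True rate, both cohorts | 38 + 12 | 48 + 15 |
|---|---|---|
| 50% | 14.5% | 16.0% |
| 55% | 16.3% | 16.9% |
| 60% | 11.9% | 10.3% |

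**False-positive rate if either may be claimed.** With both cohorts at 40%, the chance that cohort 1 or the combined test passes is 5.2% (38 + 12) or 4.6% (48 + 15). The two tests share most of their patients, so inflation is small.

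**The case against.** The strongest reply is that the readings are not equally live. Section 3.0.1 states the choice and gives reasons, 10.1 calls cohort 1 the initial proposal, and 10.2 defines the endpoint over both cohorts. Listing each cohort's rate as a secondary objective makes sense only if the primary is the combined rate; otherwise the secondaries would duplicate it. On this view the synopsis paragraph is simply text that was not updated. That largely stands, and it shows which way to reconcile. It does not remove the conflict: the synopsis is current text, 4.1 remains ambiguous, the SAP does not settle it, and no design is given for the combined endpoint.

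It may also be said that the exact 5% test is imposed on a plan whose stated rule is only a 40% threshold. The reversals occur under that threshold too.

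Three stronger readings are tempting and not supported:
- **That the primary result will be published by cohort only.** Section 14 says "The second publication will include the results of the analysis of the primary/secondary endpoints from the asymptomatic cohort and potential comparisons between both cohorts", but its first paper covers the primary and secondary endpoints and includes the symptomatic cohort. A publication plan does not define the deciding test.
- **That the endpoint was changed after most outcomes were known.** Section 3.0.1 cites a single-arm phase 2 study published in September 2022 (reference 55), and the synopsis gives "Estimated end of enrolment: 3Q 2022". This suggests a late change. But that date is an estimate, the available text does not date the change, and the number of responses then known is not given.
- **That cohort 1 must be tested first.** This would reverse the sponsor's stated choice, and the SAP already describes the database as closed, so a new testing sequence would itself be a late decision. It is an option with a trade-off, not a required correction.

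**Conclusion.** The conflict is real and lies in current text: the synopsis makes cohort 1 decisive, 3.0.1, 10.1 and 10.2 point to both cohorts combined, and the one positivity rule is ambiguous. The weight of the text favours the combined endpoint, so this is a failure to reconcile, not an open contest between three equal candidates. It matters because the verdict can reverse under either an exact 5% test or the literal 40% rule, and because cohort 1 and combined disagree in about 10–17% of trials at common true rates of 50–60%. The harm is opposite conclusions from the same data, not type I error, which stays near 5%. The evaluable-N figures rest on 20% loss in cohort 2 as well, but the full-N figures tell the same story. The disagreement rates assume independent cohorts with equal true rates.

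**What to change.** - Name one deciding population and use it in the synopsis, 4.1, 4.2, 10.1, 10.2 and the SAP. Following 3.0.1 and 10.2, that is intracranial response in both cohorts combined, in those words.
- Amend the synopsis statistics so that cohort 1 is no longer called the primary endpoint. Report cohort 1 prominently beside the combined result, as the population the trial was sized for. Keep cohort 2 alone descriptive, with an exact confidence interval.
- State that the 38/48 calculation and its 80% power apply to cohort 1, and give the critical number and power for the combined test: ≥27/50 with about 84%, or ≥33/63 with about 91%, at 60% in both cohorts.
- Mark the deciding row in SAP Tables 40 and 42.
- Disclose when the primary endpoint changed and how many day-56 responses were known then.

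**Cost.** Wording and disclosure only; no new patients or data. The sponsor gives up the ability to claim success on the other population. If the sponsor instead prefers cohort 1 first and the combined rate second, the deciding test has 78% rather than 84% power at 60% (38 and 50 evaluable), and the timing of that choice would also need to be disclosed.

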## 2.3. Melanoma with brain metastasis

Brain metastases in patients with advanced and metastatic melanoma are a frequent complication and a significant cause of morbidity and mortality in this patient population. As the incidence of brain metastases continues to increase in patients with metastatic melanoma, it is urgent that we identify effective therapies. During the past decade, management of melanoma has continued to evolve. In the era of whole-exome and next-generation sequencing, there is a requisite role for identification of driver mutations, specifically, BRAF, given the possibility for targeted therapies and the opportunity for improved survival. Moving forward, trials that investigate multimodal treatment regimens—combinations of targeted or immunotherapies with surgery or radiation—will answer additional questions regarding the optimization of management in this growing patient population.

Recent data have shown an incidence of brain metastases in  $\leq$  50% of patients with metastatic melanoma. Because this is typically a late complication of systemic disease, melanoma-related brain metastases have been associated with significant neurologic morbidity and a poor median

overall survival, with treatment, of approximately 9 months. Factors that predict survival include age, performance status, and the number of brain metastases, which are summarized as the melanoma-specific graded prognostic assessment.

Table 1. Prognostic groups for outcome after palliative treatment of brain metastases by recursive partitioning analysis.

Class	Prognostic Factors	Median survival, months
	KPS ≥70 percent	
	Age <65 years	7.1
'	Controlled primary site	
	No extracranial metastases	
III	KPS <70	2.3
II	All others	4.2

KPS: Karnofsky performance status.

Table 2. Graded prognostic assessment for brain metastases from melanoma.

Prognostic factor	Scoring criteria			Median survival (months) by score:
	0	1.0	2.0	
Karnofsky PS	<70	70-80	90-100	0-1.0 = 3.4 1.5-2.0 = 4.7 2.5-3.0 = 8.8 3.5-4.0 = 13.2
Number of brain metastases	>3	2-3	1	

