#### 6.2. Exclusion criteria

Patients meeting any of the following criteria are excluded from the study:

- 1. Uveal or mucosal melanoma.
- 2. History of leptomeningeal metastases, with the exception that they are only seen in brain MRI and the patient has ECOG 0-1 and no neurological symptoms (except for cohort 2, where symptomatic patients will be allowed if ECOG is 0-2).
- 3. Another cancer in the last two years, except for in situ carcinoma of the cervix or squamous cell carcinoma of the skin adequately treated or limited basal cell skin cancer adequately controlled. If another cancer was diagnosed in the two previous years, it should be in complete remission and without the need for any other maintenance treatment (i.e hormonotherapy, chemotherapy, targeted therapy including monoclonal antibodies and immunotherapy)
- 4. History of or current evidence of central serous retinopathy (CSR), retinal vein occlusion (RVO) or history of retinal degenerative disease (RDD).
- 5. Any previous systemic chemotherapy treatment, brain radiotherapy, targeted therapy based on BRAF and/or MEK inhibitors for locally advanced unresectable or metastatic melanoma.
- 6. History of Gilbert's syndrome.
- 7. Previous treatment with a BRAF or MEK inhibitor in metastatic setting. This treatment will be allowed in the adjuvant setting (see above). Previous treatments with immunotherapy will be allowed in both the metastatic and adjuvant setting.
- 8. Known positive serology for human immunodeficiency virus, or an active hepatitis B or hepatitis C infection, or both;
- 9. Impaired cardiovascular function or clinically significant cardiovascular diseases "Clinically significant (i.e., active) cardiovascular disease: cerebrovascular accident/stroke (< 6 months prior to enrolment), myocardial infarction (< 6 months prior to enrolment), unstable angina, congestive heart failure (≥ New York Heart Association Classification Class II), a

- LVEF < 50% evaluated as per institutional guidelines, or serious cardiac arrhythmia requiring medication or a triplicate average baseline QTc interval > 500 ms."
- 10. Uncontrolled arterial hypertension despite medical treatment.
- 11. Moderate (Child Pugh Class B) or severe (Child Pugh Class C) hepatic impairment.
- 12. Impairment of gastrointestinal function.
- 13. Neuromuscular disorders associated with high concentrations of creatine kinase.

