#### 7.1.3. INTRACRANIAL OVERALL SURVIVAL (IOS) VS SYMPTOMATIC.

Table 153: Events type OS

Symptomatic group		
Death		
Alive		

1. Pearson's Chi-squared test

Table 154: Median/mean OS (estimated by Kaplan-Meier)

	Median (months)	CI 95%	Mean	CI 95%
No				
Yes				

Table 155: OS estimated survival ratio

os	Events (%, total N)	Patients at risk	% estimated cumulative survival ratio	CI 95%
No				
At 6 months				
At 12				
months				
At 18				
months				
At 24				
months				
Yes				
At 6 months				
At 12				
months				
At 18				
months				
At 24				
months				

Figure 20: Overall survival vs Symptomatic group

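### ECOG 2 is admitted in cohort 2 only, so the SAP's unadjusted symptomatic versus asymptomatic survival estimates would partly reflect performance status; an ECOG 0-1 repeat is a cheap addition

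*Combined protocol and SAP*

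**What the plan says.** **Synopsis, Statistical methods.** Cohort 2 is exploratory. For it, "a descriptive analysis will be performed on the same variables and population as cohort 1 (N=48" is planned, and the next sentence reads: "The only difference is that the population included will be symptomatic".

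**Eligibility.** The synopsis and section 6.1 (criterion 6) both give "ECOG 0-1 in asymptomatic patients (cohort 1), 0-2 in symptomatic patients (cohort 2". Exclusion 2 in section 6.2 tolerates leptomeningeal metastases when "they are only seen in brain MRI and the patient has ECOG 0-1 and no neurological symptoms", with the rider "except for cohort 2, where symptomatic patients will be allowed if ECOG is 0-2".

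**Prognosis.** Protocol section 2.3 states: "Factors that predict survival include age, performance status, and the number of brain metastases".

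**Analysis.** SAP section 7 defines group A (cohort 2), group B (asymptomatic, with no steroids or anticonvulsants given for brain metastases) and group C (asymptomatic at study treatment, but given steroids shortly before for a symptom of the disease). A and C together are called symptomatic. SAP 7.1.3, headed "INTRACRANIAL OVERALL SURVIVAL (IOS) VS SYMPTOMATIC", and SAP 7.2.3 (iPFS) give event counts with Pearson's chi-squared test and Kaplan-Meier estimates by group. Section 2.4 of the SAP addendum does the same for ePFS and has a p-value column. SAP 7.3 tabulates response at 56 days for each group, without a test. Neither document plans a regression, stratified or ECOG-restricted analysis.

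**Publication.** Protocol section 14 foresees a second paper that may include "potential comparisons between both cohorts".

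**The concern.** The groups differ by design in a factor that the protocol itself calls prognostic. This is not a chance imbalance: no patient with ECOG 2 is eligible for cohort 1, so every ECOG 2 patient belongs to group A. If brain symptoms had no effect at all, the Kaplan-Meier estimates would still tend to look worse in the symptomatic group. Death counts as an event in the SAP's iPFS and ePFS definitions, so the same influence reaches those endpoints.

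Section 3.0.1 of the protocol justifies a primary endpoint that ignores symptoms by citing similar activity with and without them. A reader is likely to look at the group outputs with that premise in mind, and would have no version in which the ECOG range is the same on both sides. Leptomeningeal disease is a second difference, but a weaker example, because neurological symptoms from it are partly what symptomatic means.

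**Working it through.** **Plan's own figures.** The plan gives no figure for this comparison. Its sample size reproduces: n = [(1.645·√0.24 + 0.842·√0.24)/0.20]² = 37.1, so 38, and 38/0.8 = 47.5, so 48. That calculation concerns response in cohort 1 and does not enter below.

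**Where ECOG 2 can fall.** Group A is cohort 2, ECOG 0-2. Groups B and C are asymptomatic at study treatment, so on the eligibility criteria they should be ECOG 0-1. Group C therefore dilutes the ECOG 2 share of A+C.

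**Inputs.** Median survival of 9 months (protocol 2.3) and 15 patients in cohort 2 (synopsis) are stated. The hazard ratio of 1.8 for ECOG 2 is an assumption, scaled on protocol Table 1: 4.2/2.3 = 1.83 between RPA class II and class III. Also assumed are exponential survival, no symptom effect, ECOG 2 in 20%, 40% or 50% of cohort 2, and 0 or 10 patients in group C.

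**Twelve-month survival.**
- ECOG 0-1: exp(−ln2 × 12/9) = 0.397
- ECOG 2: 0.397^1.8 = 0.189
- Difference: 0.207
- Gap between B and A+C = w × 0.207, where w is the ECOG 2 share of A+C

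| ECOG 2 share of cohort 2 | w, no group C | gap (points) | w, 10 in group C | gap (points) |
|---|---|---|---|---|
| 20% | 0.20 | 4.1 | 0.12 | 2.5 |
| 40% | 0.40 | 8.3 | 0.24 | 5.0 |
| 50% | 0.50 | 10.4 | 0.30 | 6.2 |

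**Other scale.** Taking one band of protocol Table 2 instead (medians 8.8 and 4.7 months, ratio 1.87), the gap at ECOG 2 shares of 10%, 20%, 40% and 60% is 2.2, 4.4, 8.7 and 13.1 points without group C, and 1.3, 2.6, 5.2 and 7.9 points with 10 group C patients.

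**The planned test.** Survival at 24 months under the first set of assumptions is exp(−ln2 × 24/9) = 0.157 for ECOG 0-1 and 0.157^1.8 = 0.036 for ECOG 2, a difference of 0.122. Deaths by then differ between the groups by 0.20, 0.40 or 0.50 × 0.122, which is 2.4, 4.9 or 6.1 points. At 15 versus 48 patients, an uncorrected Pearson chi-squared test at 5% on those counts rejects in about 3% of trials, against about 4% with no ECOG effect.

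**The case against.** **The synopsis sentence is not an eligibility statement.** A reader might infer that it is simply false. In context it follows a remark on how cohort 2 will be analysed, and the same synopsis lists the ECOG difference. It is loose and incomplete wording; nothing is concealed.

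**No causal claim is made.** A reader might also infer that the SAP attributes any difference to symptoms. It does not say so. Cohort 2 is labelled exploratory, the A+C versus B tables are extra analyses requested by the coordinator, and section 1 of the addendum tabulates ECOG, Barthel index and metastases by these groups, so an imbalance would be visible. Section 14 speaks only of possible comparisons, and of cohorts, not of A+C against B.

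**The tests barely move, and response may not.** No hazard ratio is planned, and the chi-squared test is hardly affected. Protocol section 3 reports intracranial response of 58% in the COMBI-MB asymptomatic cohort (ECOG 0-1) and 59% in its symptomatic cohort (ECOG 0-2). That gives no sign that admitting ECOG 2 lowers response.

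**Restriction is not a full remedy.** It leaves ECOG 0 versus 1, age and number of metastases unbalanced. ECOG 2 may also be a consequence of brain symptoms, in which case restriction removes part of what one wants to see.

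All of this stands and limits the point. It does not remove the built-in imbalance in the survival estimates: a baseline table reveals it but does not show how much of the difference remains at equal ECOG range.

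**Conclusion.** The point holds as a cheap improvement. ECOG 2 can enter only the symptomatic side of the SAP's group comparisons, and nothing in either document separates it from symptoms. On the stated assumptions, 12-month survival in the symptomatic group would be about 4 to 10 points lower from ECOG alone, or 2.5 to 6 points with 10 group C patients.

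The documents give neither the ECOG 2 share nor the size of group C. They do not give the ECOG effect either: the prognostic tables use Karnofsky status, no section maps it to ECOG 2, and the graded score in Table 2 also counts brain metastases.

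The pooled primary response rate, the cohort 1 sample size and the separate cohort estimates are unaffected. The documents do not support the stronger conclusions that the planned tests would falsely declare a symptom effect, or that the plan reads performance status as one.

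**What to change.** 1. Repeat the outputs of SAP 7.1.3, 7.2.3 and 7.3 and of addendum section 2.4 in ECOG 0-1 patients, as a supplementary analysis printed beside the unrestricted version. Restriction suits the data better than a model term for ECOG 2, which would have no comparator in group B.
2. Label both versions descriptive. State beside them that ECOG 0 versus 1, age and number of metastases remain unbalanced, and that ECOG 2 may itself result from brain symptoms. The restricted version should therefore not be the sole basis for a statement about symptoms.
3. Reword the synopsis sentence so that, besides symptoms, it names the different ECOG range and the different leptomeningeal rule as they already stand in sections 6.1 and 6.2.

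The cost is one sentence and a few repeated tables, using the ECOG already recorded at baseline. The downside is a slightly smaller symptomatic group in the restricted tables.
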